A superiority trial: The hypothesis testing framework of this trial is to assess if CBD is superior to placebo in reducing FIQ-R pain in patients with fibromyalgia when assessed 24 weeks from baseline. The *P*-value will represent the probability of obtaining results as extreme as the ones observed, assuming that the null hypothesis is true (i.e., that there is no difference between groups). A smaller *P*-value indicates stronger evidence against the null hypothesis and will be applied as a threshold for determining statistical significance (1). If the two-sided *P*-value for the primary endpoint is below an α level of 5% ($P<0.05$), we will reject the null hypothesis, suggesting that the observed effect is unlikely to have occurred by random chance alone.

Randomization, allocation concealment and blinding

Stratified randomization was based on permuted blocks of up to 8 individuals; stratification was used to ensure good balance of participant characteristics in each group based on three clinically important factors. A computer-generated randomization sequence was created for each of the 8 eight strata, and consecutively patients enrolled were allocated to the corresponding treatment arms. The randomization sequence was created by an independent biostatistician using a random number generator (SAS Proc Plan), and subsequently entered in the electronic Case Report Form (e-CRF) subdivided by strata, that was developed specifically for the study, by an independent data manager. Investigators, sponsor, and outcome assessors were blinded to the permuted blocking strategy.

Sample size and power considerations

Integral to the structure of a randomized trial is the pre-established calculation of sample size, ensuring that the study is well-positioned to attain its predetermined primary objective with a high likelihood of success. In a randomized trial, the target difference refers to the desired difference between the experimental intervention and control comparator group regarding the outcome being measured (2). We decided that a difference between groups corresponding to one FIQR pain unit would correspond to a Minimal Important Difference in a population of fibromyalgia patients (3).

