For a two-sample pooled t-test of a normal mean difference with a two-sided significance level of 0.05 ($P<0.05$), assuming a common standard deviation of 2 on the 0-10 FIQR pain numeric rating scale, a total sample size of 200 assuming a balanced design (1:1), will have statistical power of 0.94 (94%) to detect a difference between the means of say 6 and 7. Even with a smaller sample of 128 patients in the ITT population assuming a balanced design (1:1), the statistical power of the suggested minimum 80 % will be obtained, to detect a difference between means of 1 on the 0-10 pain numeric rating scale. Since some attrition, drop-outs and missing data was expected during the 24-week intervention period, we decided to include 200 participants (approximately 100 in each group), in the ITT population, corresponding to a statistical power of more than 90% to detect a difference between groups that patients in the ITT population will perceive as important (4).

Statistical interim analyses and stopping guidance

No interim analyses are carried out. Due to the Covid-19 pandemic and long-term illness among the project staff, the inclusion period was extended by an extra year to allow for the inclusion of 200 participants and better ensure achieving the prespecified sample size of 200 patients in the ITT population.

Timing of final analyses

The primary and key secondary outcomes are analyzed collectively and will be reported in the primary manuscript. Final analyses will be performed blinded to group allocation and after the last patient- last- visit has been performed and all week-36 follow-up data are collected (expected in February 2024).

Box 1: Visit schedule for enrolment, interventions, and assessments. Visit “window” +/- 7 days

	STUDY PERIOD										
	Enrolment	Allocation	Post-allocation								Follow-up
Week	-8 - 0	0	1*	2	4	8*	12	16*	20	24	36
ENROLMENT:											
Informed consent	x										
Eligibility screen	x										
Medical/medicine history	x										
Physical examination	x									x	
INTERVENTIONS:											
Cannabidiol (CBD)			↔								
Placebo			↔								
Medicine dispensation		x			x		x		x		
ASSESSMENTS:											
Vital signs: BP, pulse	x	x		x	x		x		x	x	x
ECG	x										
Safety tests: Hematology, Electrolytes, ALAT, Alkaline phosphatases, Bilirubin, CRP, Urine HCG, Opioids, THC	x						x			x	
Proms: FIQ-R, PSQI, EQ5D, ADL-Q, PSEQ, DASS-21, PSS, C-SSRS, SNAQ, FSHSS		x			x		x		x	x	x

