Observation-based outcomes: AMPS, Cuff algometry, Muscle fatigability, Hair Cortisol, Weight/Height, Bioimpedance, Body fat distribution, SENS		x								x	
Compliance			x	x	x	x	x	x	x	x	
Concomitant medications	x	x	x	x	x	x	x	x	x	x	x
Adverse events		x	x	x	x	x	x	x	x	x	x

*Telephone visit

BP Blood pressure, ECG Electrocardiogram, ALAT Alanine Aminotransferase, CRP C-reactive protein, Urine Human Chorionic Gonadotropin, THC Tetrahydrocannabinol, FIQ-R Fibromyalgia Impact Questionnaire Revised, PSQI Pittsburgh Sleep Quality Index, EQ5D EuroQol Group Self-Rated Health Questionnaire, ADL-Q Activities of Daily Living Questionnaire, PSEQ Pain Self-Efficacy Questionnaire, DASS-21 Depression, Anxiety, Stress Scale, PSS Perceived Stress Scale, C-SSRS Columbia-Suicide Severity Rating Scale, SNAQ Simplified Nutritional Appetite Questionnaire, FSHSS Fibromyalgia Sensory Hypersensitivity Scale, AMPS Assessment of Motor and process skills, SENS MOTION® activity measurement system.

Statistical principles

Confidence intervals and P-values

All 95% confidence interval and *P* values will be two sided, and the level of statistical significance for the primary endpoint was *a priori* defined as a *P*-value < 0.05. We will not apply explicit adjustments for multiplicity; instead, we will analyze and interpret the key secondary outcomes using the Hochberg sequential procedure: All the multiple tests for secondary outcomes are performed, and the resultant *P*-values are ordered from largest to smallest on a list (5). If the largest observed *P*-value is less than 0.05, then all the tests are considered statistically significant. Otherwise, if the next largest *P*-value is less than 0.05/2 (0.025), then all the tests except the one with the largest *P*-value are considered significant. If not, and if the third *P*-value in the list is less than 0.05/3 (0.017), then all the tests except those with the largest 2 *P*-values are considered significant. This will be continued until all the comparisons are made. This approach uses progressively more stringent statistical thresholds (i.e., the most stringent one being the Bonferroni threshold).

Adherence and protocol deviations

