12.2 Statistical analyses

The details for the statistical analyses plan (SAP) will be determined prior to the completion of data collection and before the data analyses are initiated [64]. The prespecified efficacy analyses will be based on the data for full analysis set; the intention-to-treat (ITT) population, which includes all participants that are assessed and randomized at baseline. In the case of missing data at week 24, the baseline values will be carried forward and included in the of trial analyses.

The primary analyses will be the comparison between cannabidiol 50 mg and placebo, using a mixed linear repeated-measures ANCOVA model with treatment, stratifying factors, and weeks from baseline as fixed effects; in order to reduce the random variation, we will adjustment for the level at baseline as a covariate. From this model the potential observed differences in pain intensity (FIQ-R NRS) and the secondary continuous outcomes will be estimated together with the associate 95% confidence interval and the p-value corresponding to the test of the hypotheses of no difference between treatments (i.e. the null hypothesis).

To establish the efficacy of cannabidiol 50 mg compared to placebo in patients with fibromyalgia, the key secondary endpoints are tested in a hierarchical manner in the order in which endpoints are presented. Cannabidiol will be considered statically significantly better than placebo with respect to change in pain intensity FIQ-R NRS if the null hypothesis is rejected (p<0.05). Categorical changes for dichotomous end points will be analyzed with the use of logistic regression with the same fixed effects and covariates as

AUTHOR: [name], The Parker Institute, Copenhagen University Hospital

DATE: 2020-12-14

Protocol number P142; Version: 4; EudraCT: 2019-002394-59, Regional Ethical Committee Journal Number H-20047715. ClinicalTrials.gov Identifier:

the respective ANCOVA for continuous outcomes (see above). Sensitivity analyses will be performed to assess the robustness for the primary analyses, including a 'non-responder imputation', 'multiple imputation techniques ', and a 'per protocol analysis'.

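### Nothing in the SAP makes the key secondary tests conditional on the pain result, so the chance of a false significant claim over primary plus key secondaries is about 6.6% to 9.7%, not 5%

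*SAP*

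**What the plan says.** **SAP, primary.** Under Framework, the null hypothesis is rejected if the two-sided P-value "for the primary endpoint is below an α level of 5" per cent. The power calculation is likewise "with a two-sided significance level of 0.05".

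**SAP, key secondaries.** Under Confidence intervals and P-values, the plan states that "we will analyze and interpret the key secondary outcomes using the Hochberg sequential procedure". The procedure starts at the full level: if the largest P-value "is less than 0.05, then all the tests are considered statistically significant". The thresholds then fall to 0.05/2, 0.05/3 and so on. The primary is not in this family. No condition on the primary is given; the text says "All the multiple tests for secondary outcomes are performed".

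**SAP, other statements.** The same section, and Methods in the Summary, say that no explicit multiplicity adjustment will be made. The Summary adds a loose definition of significance for secondary outcomes, namely P < 0.05.

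**Protocol version 4, section 12.2.** To establish efficacy, "the key secondary endpoints are tested in a hierarchical manner in the order in which endpoints are presented". The last paragraph of the same section leaves the multiplicity detail to the SAP and speaks of a narrative adjustment, with Bonferroni as the example.

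**The concern.** The plan has two routes to a significant result, each with its own 5%, and neither depends on the other. Suppose pain gives P = 0.40 and one of nine key secondaries gives P = 0.004. The strictest Hochberg threshold is 0.05/9 = 0.0056, so that secondary is statistically significant under the SAP as written, although the trial has failed on its primary endpoint.

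This matters because the SAP's stated aim is superiority on relevant outcomes, not on pain alone, and because protocol section 12.2 links the key secondaries to establishing efficacy. A reader of the main paper could fairly take a Hochberg-significant secondary as a confirmed effect. The SAP does not say whether that reading is intended.

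**Working it through.** **Inputs**
- Primary: two-sided 0.05 (SAP, Framework).
- Key secondary family: Hochberg at 0.05, ungated (SAP, Confidence intervals and P-values).
- Number of key secondary tests: nine rows in SAP Table 2, because activities of daily living is split into AMPS motor, AMPS process and ADL-Q. It is seven if that domain is counted once.
- Correlation between outcomes: not given. A common value from 0 to 0.9 is assumed.

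**Step 1: the plan's own figure.** The documents state power for the primary but no overall error rate. For a difference of 1, SD 2 and 100 per arm, the noncentral t calculation gives 0.940, against the stated 0.94. With 64 per arm it gives 0.801, against the stated 80%. Both reproduce.

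**Step 2: simple limits.** With all null hypotheses true and no gate:
- Upper bound: 0.05 + 0.05 = 10.0%.
- If the two families are independent and each uses its full 5%: 1 − 0.95² = 9.75%.

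**Step 3: simulation.** This used 1,000,000 trials per setting under the global null, with equally correlated normal test statistics, the primary at two-sided 0.05 and Hochberg at 0.05 on the rest. A false result in either direction is counted.

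| Assumed correlation | Hochberg family alone (9 tests) | Any false claim, no gate (9 tests) | Any false claim, no gate (7 tests) |
|---|---|---|---|
| 0 | 4.9% | 9.7% | 9.6% |
| 0.2 | 4.7% | 9.3% | 9.3% |
| 0.3 | 4.6% | 9.0% | 9.0% |
| 0.5 | 4.0% | 7.9% | 8.0% |
| 0.7 | 3.0% | 6.6% | 6.7% |
| 0.9 | 2.0% | 5.2% | 5.3% |

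Counting seven tests or nine makes almost no difference.

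**Step 4: with a gate.** If the key secondaries can yield a claim only after primary P < 0.05, no false claim can occur under the global null unless the primary itself is falsely significant. The figure is then 5.0% at every correlation.

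**Step 5: does Hochberg cause the excess?** Take the protocol's hierarchy literally, as a fixed sequence among the secondaries that is not tied to the primary. A false claim then needs either the primary or the first secondary below 0.05. That gives 9.75% at correlation 0 (1 − 0.95²), 9.5% at 0.3, 9.1% at 0.5 and 8.4% at 0.7. None of these is lower than the Hochberg figures in the table, so the excess comes from the missing gate.

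**Step 6: the Summary's loose rule.** Unadjusted P < 0.05 on 1 + 9 independent tests gives 1 − 0.95¹⁰ = 40%. The simulated value at correlation 0.5 is 29%.

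**The case against.** There is a serious case on the other side, and much of it stands.

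- **The primary is protected.** The SAP's hypothesis-testing framework is about pain alone, and that error is 5% with or without a gate. Hochberg also controls the secondary family under independence or positive dependence. The documents never promise 5% over the combined set, and whether the two should share it is partly convention. This stands, and it limits the point to the combined error.
- **Hochberg is a permitted choice.** A reader might infer that the SAP inflated the error by dropping the protocol's hierarchy. The documents do not support this. Section 12.2 implies a gate on pain but does not state one, and Step 5 shows that an ungated hierarchy does no better. The section's closing paragraph hands the method to the SAP and mentions Bonferroni, which is Hochberg's strictest threshold.
- **No unannounced departure can be shown.** A reader might also infer that the SAP departed silently from its protocol. The SAP cites protocol version 5 (17.08.2023), but the protocol available is version 4 (2020-12-14). The change may have been made in version 5.
- **Joint analysis is not a joint family.** The sentence "The primary and key secondary outcomes are analyzed collectively and will be reported in the primary manuscript" stands under Timing of final analyses. It concerns when and where results appear and does not define a testing family, so nothing here rests on it.

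What the objection does not answer is that the SAP has a formal rule for calling key secondaries statistically significant and does not say what that means when pain is not significant. Since the protocol defers multiplicity to the SAP, that is where the statement belongs.

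**Conclusion.** The point holds as a missing gate. Followed as written, the SAP lets a trial that fails on pain declare a key secondary significant through a second full 5%. Over primary plus key secondaries the chance of a false claim is about 6.6% to 9.7% for assumed common correlations of 0.7 down to 0. It is 8% to 9% at 0.3 to 0.5, and 10% is the ceiling. With a gate it is 5.0%. These figures assume that CBD has no effect on any of the outcomes and that all pairs of outcomes are equally correlated.

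The conflict inside the SAP between Hochberg and the loose P < 0.05 is a separate defect and, if the loose rule were applied, the larger one. The primary analysis is not affected by either, so this should be corrected but does not undermine the trial's main test.

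**What to change.** 1. In the SAP, Confidence intervals and P-values, add: *Hochberg at 0.05 is applied to the key secondary outcomes (the nine rows of Table 2) for formal claims only if the primary two-sided P-value is below 0.05. Otherwise their estimates, confidence intervals and P-values are reported as exploratory.*
2. Delete the loose P < 0.05 definition for secondary outcomes in the Summary, and reword the statements that no explicit adjustment is made, since Hochberg is one.
3. State that this rule replaces the hierarchical order in section 12.2 of protocol version 4.

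The cost is a few sentences. The primary keeps its 0.05 level and its 94% power, and every estimate is still reported. The one real loss is that no formal key secondary claim can be made if pain is not significant. The SAP is dated 03.01.2024 and expected the last follow-up data in February 2024, so on that timetable the change could be made before the final analysis.

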The treatment period begins with a two-week titration phase, starting with a daily dosage of 10 mg CBD or placebo at week 0. Subsequently the dosage is titrated up by 10 mg every third day until a daily dosage of 50 mg is reached. Dose escalation is based on safety and tolerability, and if the planned dose escalation is not feasible, then delayed increments are allowed. Subjects will be maintained at the highest tolerated dose level, through-out the study. The per-protocol population is represented by participants who have been compliant with the schedule of activities and has ingested the project medication throughout the study at the highest tolerated level. Compliance is monitored by counting the number of non-ingested tablets. Compliance is calculated as % compliance number of tablets ingested from week 2 to week 24/ (number of days week 2-24 x maintenance dose/50 mg) x 100%. In addition, the use of opioids during the intervention period will be considered a protocol deviation.

Analysis populations

Intention-to-treat population

The appropriate use of a randomized trial design enables estimation of the average causal effect. The main analyses in the CANNFIB trial will be based on the Intention to Treat (ITT) population. In the context of a randomized trial, the average causal effect is estimated through statistical analysis, comparing the average outcomes of the treatment group with those of the control group. Randomization in trials helps ensure that observed differences in outcomes between the groups can be attributed to the treatment rather than confounding variables. The ITT population includes all participants according to their randomized treatment assignment, while the average causal effect measures the average impact of a treatment on the outcome of interest in a study population. Thus, the ITT principle asserts the effect of a treatment policy (the pre-planned treatment regimen), rather than the actual treatment given, thus, it is independent of treatment compliance. Accordingly, participants in the CANNFIB trial allocated at baseline will be followed-up, assessed, and analyzed as members of their respective allocated group, regardless of their compliance and adherence to the planned course of treatment, and even independent of withdrawals (i.e., the ITT Population) (6).

Per Protocol Population

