8.4. Study drug use, content and handling

Cannabidiol will be administrated to the participants orally in tablet form. Participants will start with 10 mg daily and the dose will be escalated every third day until the maximum dosage of 50 mg is reached (after two weeks). Dose escalation will be based on safety and tolerability, and if dose escalation is not feasible, then delayed increments are allowed. Subjects will be maintained at the highest tolerated dose level. However, reduction of the achieved maintenance level will lead to study discontinuation. The dosage of 50 mg as the daily intake during the study period, is decided based on clinical experience from private pain clinics from where medical cannabis is prescribed in Denmark (Clinic Horsted), and on dialogue with the pharmacists at Glostrup pharmacy, who will supply the investigational medicinal product and placebo. Glostrup pharmacy is experienced in producing cannabidiol pills for research purposes, and "cannabidiol" placebo pills that are identical in appearance, taste, and smell. Glostrup pharmacy will be responsible for the labelling of the cannabidiol and placebo tablet packages with a unique Dispensing Unit Number (DUN). The investigating site will ensure proper storage of the trial products, in a locked and secure temperaturecontrolled room. A non-blinded, non-investigator will ensure that participants are receiving the study drug or placebo according to the treatment allocation by parring DUN numbers and the recipient patient numbers in the e-CRF system. One investigator will be responsible for drug accountability. For each patient treated, the DUN number of the package will be documented, and the patients will be asked to return the empty packages after use for accountability. Proper destruction of unused drugs will be ensured.

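### The SAP's compliance formula counts tablets against a 50 mg unit, so it overstates compliance for patients kept below 50 mg, and for everyone if smaller tablets are counted

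*SAP*

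**What the plan says.** The SAP section on adherence and protocol deviations describes a two-week titration from 10 mg a day, with the dose "titrated up by 10 mg every third day until a daily dosage of 50 mg is reached". Slower escalation is permitted: "if the planned dose escalation is not feasible, then delayed increments are allowed". It then states: "Subjects will be maintained at the highest tolerated dose level, through-out the study". Maintenance below 50 mg is therefore foreseen, and the formula itself carries a maintenance-dose term.

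Compliance is monitored by counting tablets that were not taken. The percentage has "number of tablets ingested from week 2 to week 24" as its numerator and "number of days week 2-24 x maintenance dose/50 mg) x 100" per cent as the remainder.

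Protocol section 8.4 confirms that the drug is given as oral tablets. Neither document gives the mg content of a tablet. (The protocol supplied is version 4; the SAP cites version 5.)

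The per-protocol set is described in words three times in the SAP: under Adherence and protocol deviations, under Per Protocol Population and under Missing Data. None of these gives a compliance percentage. The per-protocol analysis is one of the two sensitivity analyses listed under Missing Data and is reported in Appendix Table 2b.

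**The concern.** A compliance percentage should read 100 when a patient takes everything assigned. Here the numerator counts tablets and the denominator counts 50 mg units. The two agree only for a 50 mg tablet, and whole 50 mg tablets cannot supply a daily dose of 10, 20, 30 or 40 mg. The maintenance-dose term exists to handle patients below 50 mg, and that is where the formula goes wrong.

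This is the only quantified measure of drug intake in the documents. If it is used as written, reported compliance may exceed 100% for adherent patients, and poor adherence may look complete. A threshold applied to the raw figure could then admit patients to the per-protocol set who took little of their medication.

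**Working it through.** The plan states no compliance result, so there is no figure to reproduce. The check evaluates the formula for patients whose true adherence is known.

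**Inputs**
- Days: the formula uses "number of days week 2-24", which is (24 − 2) × 7 = 154.
- Assigned daily dose D: 10, 20, 30, 40 or 50 mg, from the SAP's 10 mg steps and tolerated-level rule.
- Tablet strength s: not stated, so treated as an assumption over 5, 10, 20, 25 and 50 mg.

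**1. Full adherence, one tablet strength.** Tablets taken = 154 × D/s. SAP denominator = 154 × D/50. Score = 100 × (154 × D/s) / (154 × D/50) = 100 × 50/s. The dose cancels, leaving:

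| Assumed strength | Score at full adherence |
|---|---|
| 5 mg | 1000% |
| 10 mg | 500% |
| 20 mg | 250% |
| 25 mg | 200% |
| 50 mg | 100% |

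The 20, 25 and 50 mg rows are arithmetic only. Those strengths used alone cannot deliver every 10 mg step in whole tablets.

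**2. A bound that needs no strength.** A fully adherent patient taking whole tablets daily takes at least one a day, so at least 154 in all. The score is then at least 100 × 154 / (154 × D/50) = 100 × 50/D:

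| Dose | SAP denominator | Minimum score |
|---|---|---|
| 40 mg | 154 × 0.8 = 123.2 | 154/123.2 = 125% |
| 30 mg | 154 × 0.6 = 92.4 | 154/92.4 = 167% |
| 20 mg | 154 × 0.4 = 61.6 | 154/61.6 = 250% |
| 10 mg | 154 × 0.2 = 30.8 | 154/30.8 = 500% |

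**3. If 10 mg tablets are counted.** Full adherence at 50 mg is 770 tablets: 770/154 = 500%. At 30 mg it is 462 tablets: 462/92.4 = 500%. A patient on 50 mg who took 20% of the tablets took 0.2 × 770 = 154, and 154/154 = 100%.

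**4. If strengths are mixed.** Suppose 50 mg tablets are used at 50 mg and 10 mg tablets below it. A fully adherent patient on 50 mg scores 154/154 = 100%. A patient on 40 mg who took half of the 616 assigned tablets scores 308/123.2 = 250%. The less adherent patient ranks higher.

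**5. Late escalation.** Suppose a patient is on 40 mg in weeks 2–4 (14 days), then on 50 mg (140 days), and takes every dose. In 50 mg units, using the final maintenance dose, the score is (14 × 40/50 + 140)/154 = 151.2/154 = 98.2%. This is a small error in the other direction.

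**6. Computed in mg.** With 10 mg tablets, full adherence at 50 mg gives 770 × 10 / (154 × 50) = 7700/7700 = 100%. At 30 mg it gives 462 × 10 / (154 × 30) = 4620/4620 = 100%. In step 5, mg taken and mg assigned are both 14 × 40 + 140 × 50 = 7560, which gives 100%.

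**The case against.** The strongest defence is that the denominator counts 50 mg equivalents. If the numerator is in the same unit, full adherence gives 100% at any constant maintenance dose, and the only gap is an unstated unit. The protocol's budget (section 14) lists cannabidiol 50 mg, which fits a 50 mg unit, though it may mean the daily dose. This defence stands for patients on 50 mg who take 50 mg tablets. It does not stand below 50 mg: the numerator is written as a tablet count, and neither document mentions splitting tablets or converting counts.

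It is also fair that the per-protocol analysis is declared secondary and likely biased, that protocol section 8.3 plans for participants to stay on 50 mg, and that the number maintained below 50 mg is unknown.

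A reader might infer four stronger things that the documents do not support:
- *Every adherent patient scores 500%.* This needs 10 mg tablets to be the ones counted, which neither document states.
- *The per-protocol set cannot be identified because of the scaling.* With one strength the error is a constant factor that preserves ranking and can be divided out. The direct obstacle is that no cut-off ties the percentage to membership.
- *The error differs between arms.* That would need both mixed strengths and different tolerated doses by arm. Neither is shown.
- *Leftover tablets are not returned.* Protocol section 8.4 says "the patients will be asked to return the empty packages after use for accountability", but it also provides for destroying unused drug, and the SAP says that tablets not taken are counted.

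**Conclusion.** The formula is wrong as written, and stating the tablet strength would not by itself repair it for patients maintained below 50 mg. The minimum overstatement for those patients rests on two assumptions: whole tablets, and at least one taken every day. For patients on 50 mg the result runs from correct (50 mg tablets) to a fivefold overstatement (10 mg tablets), or more with smaller tablets. Loss of ranking is conditional on a mixed-strength supply.

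The reach is limited to compliance reporting and the per-protocol sensitivity analysis. The ITT primary analysis does not use the figure. The point is worth correcting because the correction is nearly free and this is the only numerical drug-intake measure in the plan.

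**What to change.** State in the SAP the strength or strengths of the tablets dispensed, and replace the formula with:

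compliance % = (tablets ingested in weeks 2–24 × tablet strength in mg) / (sum over those days of the assigned daily dose in mg) × 100

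Add up the numerator over strengths if more than one was dispensed. For placebo, use the nominal strength of the matching tablet. Summing the assigned dose day by day also deals with increments that came after week 2.

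Before unblinding, state the compliance cut-off that decides per-protocol membership, and use the same rule wherever the SAP defines that set.

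The cost is a short SAP edit and a recalculation, provided that tablet counts and assigned doses were recorded. The documents do not confirm that the assigned dose was recorded for each day, so this should be checked first.
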